13. STATISTICS

13.1. Determination of Sample Size

The sample size was set to 60 (15 active vaccine recipients in each group and 5 placebo recipients in each group) to allow adequate identification of potential toxicities and document safety. The study design was developed as a compromise between the costs of vaccine manufacturing and regulatory clearance and the need to detect safety. Within each group: The study is planned with 15 experimental volunteers and 5 control volunteers. With expectation that significant adverse event in the control volunteers to be very small (<0.1%), we will be able to detect a minimal SAE rate of 73.5% among experimental volunteers with power of 0.8. The Type I error probability associated with this test of the null hypothesis that the SAE rates for experimental and control subjects are equal is 0.05. We used Fisher's exact test to evaluate this null hypothesis. Pooled across groups: The study is planned with 45 experimental volunteers and 15 control volunteers. With expectation that significant adverse event in the control volunteers to be very small (<0.1%), we will be able to detect a minimal SAE rate of 36.8% among experimental volunteers with power of 0.8. The Type I error probability associated with this test of the null hypothesis that the SAE rates for experimental and control volunteers are equal is 0.05. We used Fisher's exact test to evaluate this null hypothesis.

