2. SYNOPSIS

Name of Sponsor/Company: Sponsor: Institute of Human Virology Manufacturer: Profectus Biosciences	
Name of Investigational Product: IHV01	
Name of Active Ingredient: Full Length Single Chain (FLSC), Aluminum Phosphate	
Title of Study: A Phase I Safety and Immunogenicity Trial of IHV01, in HIV-1 Uninfected Volunteers	
Study center(s): Institute of Human Virology	
Principal Investigator: [name], M.D. Investigators: [name]. [name].	
Studied period (years): 1 year Estimated date first patient enrolled: November 2015 Estimated date last patient completed: May 2018	Phase of development: I
Objectives: Primary: To evaluate the safety and tolerability of intramuscular administration of the IHV01 at three different doses. Secondary: To evaluate the immunogenicity of three different doses of the IHV01, a full length single chain (FLSC) gp120-CD4 complex vaccine. This will be assessed by the following parameters: 1) anti-FLSC antibodies, and 2) anti gp-120 (BaL), and 3) competitive titers to CD4i epitopes.	
Methodology: Single center, randomized, dose escalation, placebo-controlled, double-blind trial	
Number of patients (planned): 60	
Diagnosis and main criteria for inclusion: Inclusion/Exclusion Criteria as in Section 7.1 and Section 7.2 .	
Investigational product, dosage and mode of administration: IHV01 in sequential dose escalation of 75 ug, 150 ug and 300 ug administered intramuscularly.	
Duration of treatment:	

Volunteers will be immunized with candidate vaccine or placebo on Days 0, 28(week 4), 56(week 8), and 168(week 24). Volunteers will continue to undergo active protocol follow up visits on Days 182(week 26), 196(week 28), 252(week 36), 294 (week 42) and 336 (week 48). The total trial time expected per volunteer is 48 weeks. The protocol recruitment period is expected to be approximately 36 weeks. The total trial duration is estimated to be approximately 72-96 weeks.

Reference therapy, dosage and mode of administration:

Placebo consisting of preservative free normal saline in volumes equal to the investigational product administered intramuscularly.

Criteria for evaluation:

Safety:

1. Monitoring and assessment of hematological, chemical, and immunologic parameters (See [Section 11.1.5](#), [Section 12.1](#), and [Table 4](#)).
2. Monitoring participants for local and systemic adverse reactions after each injection and for 12 months after the first injection ([Section 11.2](#)).
 - a. Local reactogenicity signs and symptoms

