6.3. Treatment Assignment

The volunteers in this study will enroll in each group of the study sequentially as this is a dose escalation study. Each volunteer will undergo randomization as described in [Section 8.4](#). Each group will be fully enrolled prior to the enrollment of the next group. The description of the FLSC vaccine is noted in [Section 8](#) and [Section 9](#) and the clinical formulation of the products are listed in [Section 9](#). Volunteers in all arms will be immunized by intramuscular injection on Days 0, 28 (week 4), 56 (week 8), and 168 (week 24). Following completion of the immunization schedule, all volunteers will be followed (for an additional 24 weeks) until the end of the trial at 48 weeks as detailed in [Section 6.1.1.3](#).

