8.4. Randomization and Blinding

Volunteers will be randomized using block randomization in a 3:1 ratio of FLSC:placebo. They will be block randomized in groups of 4 with each study group. This will be done by the research pharmacist utilizing random # generator called Stat Trek. There will be 5 groups of 4 volunteers in each randomized block (each block will have 3 FLSC recipients and 1 placebo recipient).

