13.2. Statistical Methods

Each safety parameter assessed will be compared between vaccine recipients and placebo recipients as determined by Student's T test *and chi-square analyses*. In addition safety parameters will be compared between vaccine dose groups as well as to placebo recipients. In addition each volunteer will serve as their own control for the occurrence of toxicity. Adverse reaction as defined in Appendix 1 and 3 will be reported independent of a statistical association.

Immunogenicity parameters will be compared using response and non-response as well as mean medium and geometric mean titers between vaccine recipients and placebo recipients as determined by Student's T test *and chi-square analyses*. Immunogenicity parameters will be compared between vaccine dose groups as well as between each to placebo recipients. Exploratory analyses will be performed (e.g., examination of frequency distributions, modality of distributions, kurtosis and skewness, etc.) for all variables collected before subjecting the values to statistical analysis. Cross-sectional parametric and non-parametric analyses will be conducted on variables exhibiting normal and non-normal distributions, respectively, to examine differences and trends among treatment categories.

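### The overall vaccine-placebo test ignores the dose groups within which volunteers are randomised, and the plan does not say which placebo recipients each dose is compared with

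*Combined protocol and SAP*

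**What the plan says.** **Randomisation.** Section 8.4 says "Volunteers will be randomized using block randomization in a 3:1 ratio of FLSC:placebo" and "They will be block randomized in groups of 4 with each study group". Five blocks of four give 15 vaccine and 5 placebo recipients in each group.

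**Sequence.** Section 6.3 says "Each group will be fully enrolled prior to the enrollment of the next group". Section 6.4 holds the next group until the DSMB has reviewed data through visit 4 from the 20 volunteers in the group below.

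**Placebo.** The Synopsis describes "Placebo consisting of preservative free normal saline in volumes equal to the investigational product administered intramuscularly". Table 7 (Section 9.4.4) gives 0.25, 0.5 and 1.0 ml for Groups 1, 2 and 3.

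**Sample size.** Section 13.1 gives two calculations, both attributed to Fisher's exact test with power 0.8, Type I error 0.05 and a control rate below 0.1%:
- "Within each group: The study is planned with 15 experimental volunteers and 5 control volunteers", with a detectable rate of 73.5%.
- "Pooled across groups: The study is planned with 45 experimental volunteers and 15 control volunteers", with a detectable rate of 36.8%.

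**Analysis.** Section 13.4 compares vaccine with placebo recipients by Fisher's exact test, with Type I error capped at 5%. Section 13.2 adds that "safety parameters will be compared between vaccine dose groups as well as to placebo recipients", and Section 13.5 plans dose-versus-placebo comparisons for immunogenicity. No section makes dose group a stratum or a factor in a vaccine-placebo test. Sections 13.2 and 13.5 do not say whether a dose is set against its own 5 placebo recipients or all 15.

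**The concern.** Each dose group is its own small randomised trial, and an analysis would normally respect that. Background reaction rates could differ between cohorts for three reasons found in the protocol: the injected volume differs, the cohorts enrol at different times, and Section 8.4.1 leaves volunteers and investigators aware of the dose group, so reporting of symptoms may shift with it.

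Two things are at stake. The overall test may give away power by ignoring known strata. More importantly, Section 4.2 makes the choice of dose a purpose of the trial, based on safety and immunogenicity. The dose-versus-placebo comparisons feed that choice, and two analysts could use different placebo comparators and both claim to have followed the plan.

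**Working it through.** **1. The plan's own figure.** Inputs from Section 13.1: 15 controls, ratio k = 3, power 0.8, Type I error 0.05 (taken as two-sided, which reproduces the figures), control rate p0 = 0.001 (the stated upper limit), vaccine rate p1 = 0.368.

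With d = p1 − p0 = 0.367 and p̄ = (p0 + 3p1)/4 = 0.27625, the number of controls before continuity correction is

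n = [1.960·√(p̄(1−p̄)(1+1/3)) + 0.8416·√(p0(1−p0) + p1(1−p1)/3)]² / d² = (1.0120 + 0.2358)² / 0.1347 = 11.56.

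Continuity correction: (n/4)·[1 + √(1 + 2(1+1/3)/(n·d))]² = 2.89 × 2.276² = 14.97, that is 15 controls. The same formula at 73.5% gives 4.99, that is 5 controls. Both stated figures reproduce, as continuity-corrected approximations.

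**2. Is the overall comparison biased?** Let p1, p2, p3 now be the background rates in the three cohorts, with no vaccine effect. The expected pooled vaccine rate is 15(p1+p2+p3)/45 and the expected pooled placebo rate is 5(p1+p2+p3)/15. Both equal the mean rate, so the difference is zero whatever the cohort rates.

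**3. What ignoring the strata does.** The pooled test behaves as if the variance were p̄(1−p̄), where the within-cohort variance is the mean of p(1−p). At assumed rates 5/20/40%, p̄(1−p̄) = 0.2167 × 0.7833 = 0.170, and the mean within-cohort value is (0.0475 + 0.16 + 0.24)/3 = 0.149. The pooled test is therefore conservative.

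The table compares two-sided pooled Fisher (45 v 15) with an exact conditional test stratified by dose group. The stratified test refers total vaccine events to the sum of three hypergeometric distributions, given each group's event total. All results come from full enumeration at 0.05. Rates are for Groups 1/2/3; every rate except the first row's is assumed, because the documents give none by cohort.

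| Vaccine rates | Placebo rates | Pooled | Stratified |
|---|---|---|---|
| 36.8% in each (plan's inputs) | 0.1% in each | 94.1% | 95.1% |
| 30/50/70% | 5/15/35% | 55.8% | 59.5% |
| 32/60/90% | 2/30/60% | 43.8% | 57.8% |
| 30/40/50% | 5% in each | 81.4% | 80.7% |
| 5/20/40% (no effect) | 5/20/40% | 2.0% | 3.0% |

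**4. One dose against all 15 placebo recipients.** With no vaccine effect, the expected difference for group g is its own rate minus the mean of the three. At 10/10/30% the mean is 16.7%, so Group 3 is off by 30 − 16.7 = 13.3 points. At 5/20/40% the mean is 21.7%, so the three groups are off by −16.7, −1.7 and +18.3 points. False-positive rates by two-sided Fisher:

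| Assumed background | 15 v pooled 15 (Groups 1, 2, 3) | 15 v own 5 (Groups 1, 2, 3) |
|---|---|---|
| 10/10/30% | 2.0%, 2.0%, 5.9% | 0.5%, 0.5%, 1.8% |
| 5/20/40% | 9.8%, 1.5%, 8.4% | 0.1%, 1.3%, 2.2% |

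**The case against.** The strongest reply is that the explicit pooling in Section 13.1 is all vaccine against all placebo, which the fixed 3:1 ratio protects, and that the same section also sizes the own-group 15 v 5 comparison. That stands. A reader might infer that pooling confounds vaccine with cohort; the constant 15:5 split rules that out, apart from slight imbalance if volunteers are replaced under Section 6.1.1.5. A reader might also infer that the plan tests each dose against all 15 placebo recipients. No section says so. Sections 13.2 and 13.5 are silent, and Section 12.2.5, which describes vaccine against placebo as Arms 1 and 2 against Arm 3, does not settle it.

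The size is also fairly challenged. The documents give no saline reaction rates by cohort, stratifying gains one point of power at the plan's own inputs, and 10/10/30% only just passes 5%. Larger errors need cohort rates much further apart than anything the documents support.

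Section 13.6 says a significance level is not pertinent, and escalation and halting rest on DSMB review and event counts. That lowers the stakes but does not remove them, since Section 13.4 still sets a 5% limit and the dose is to be chosen from these data.

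Finally, own-group comparisons are weak. With vaccine at 70% and placebo at 30% in Group 3 (assumed), enumeration of Fisher's test at 15 v 5 gives about 26% power. Pooled placebo therefore has a place, as a supportive display.

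**Conclusion.** The point holds as a modest analysis improvement and a needed clarification. The overall vaccine-placebo comparison is valid but ignores the randomisation strata. The cost is power only, and only if background rates differ by cohort: 1 point at the plan's inputs, about 4 points at 5/15/35%, and 14 points at the far more divergent 2/30/60%. When placebo rates are equal at 5%, stratifying loses 0.7 of a point.

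The dose-versus-placebo comparisons are the more consequential gap, because the plan leaves the comparator open. If it were all 15, the false-positive rate could exceed the limit in Section 13.4, by a little at 10/10/30% (5.9%) and by more at 5/20/40% (8.4% and 9.8%). Against the group's own five it stays at or below 2.2% in these scenarios. These sizes rest on assumed cohort rates; the unprotected status of that contrast does not.

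**What to change.** In Sections 13.2, 13.4 and 13.5:

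- Stratify the overall vaccine-placebo test by dose group: an exact stratified test for binary endpoints, and dose group as a factor for continuous endpoints such as log titres.
- Name the concurrent placebo recipients of the same group as the comparator for each dose, in line with the within-group calculation in Section 13.1.
- Show each dose beside pooled placebo as supportive only, with placebo results listed by group.

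This changes wording and uses standard software. The sample size, visits and conduct stay as they are. The price is that each own-group comparison has only 5 controls and low power, and that the stratified test may lose under 1 point of power when cohorts do not differ. Comparisons between dose groups remain non-randomised whichever placebo is used, and should be described that way.

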13.4. Primary Criterion Analysis

The primary reactogenicity (safety) endpoints are occurrence of severe systemic and severe local reactions.

Separate assessments of systemic and local reactions will be performed. Each safety parameter assessed will be compared between vaccine recipients and placebo recipients as determined by Fisher exact test with a Type I error of no greater than 5%.

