13.6. Level of significance

Level of significance is not pertinent to this trial as it is a Phase 1 safety and immunogenicity trial.

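### Section 13.1: the pooled detectable rate of 36.8% matches a continuity-corrected approximation, not the Fisher's exact test it names, which reaches 80% power at 31.6% (minor)

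*Combined protocol and SAP*

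**What the plan says.** Section 13.1 gives two power statements, each at a type I error of 0.05 with a control event rate expected to be below 0.1%. Within a dose group (15 vaccine, 5 placebo): "we will be able to detect a minimal SAE rate of 73.5% among experimental volunteers with power of 0.8". Pooled over the three groups (45 vaccine, 15 placebo): "we will be able to detect a minimal SAE rate of 36.8% among experimental volunteers with power of 0.8". The per-group error rate is attached to the "null hypothesis that the SAE rates for experimental and control subjects are equal is 0.05", and the pooled statement is parallel. Each is followed by "We used Fisher's exact test to evaluate this null hypothesis".

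The section does not say whether the test is one- or two-sided, how a two-sided Fisher p-value is defined, or whether power came from enumeration or a formula. Section 13.4 plans Fisher tests at a type I error of at most 5% for the primary safety comparison. Section 13.6 says: "Level of significance is not pertinent to this trial as it is a Phase 1 safety and immunogenicity trial".

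**The concern.** A colleague who checks 13.1 with an exact Fisher calculation will not recover the pooled figure, and nothing in the document explains why. The two rates are the only numerical justification for the sample size in that section. If they are described as the minimal rates detectable with 80% power by Fisher's exact test, they should be that test's rates. What is at stake is the accuracy of the power statement. No decision in the trial depends on it.

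**Working it through.** **Inputs.** From 13.1: 15 vs 5 and 45 vs 15 (3:1), type I error 0.05, power 0.80, control rate below 0.1%. I take p0 = 0.001, the upper bound. Two-sided testing is an assumption, natural because the null is equality; one-sided is shown as well.

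**1. Reproducing the stated figures.** Use the two-proportion formula with continuity correction, with d = p1 − p0 and p̄ = (p0 + 3p1)/4.

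Uncorrected number of controls: m = [1.960·√(4p̄(1−p̄)) + 0.842·√(3p0(1−p0) + p1(1−p1))]² / (3d²).

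Corrected number of controls: n0 = (m/4)·[1 + √(1 + 8/(3md))]². Vaccinees = 3·n0.

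- p1 = 0.735: d = 0.734, p̄ = 0.5515, m = (1.9495 + 0.3743)²/1.6163 = 3.341, n0 = 4.992, vaccinees = 14.98 (planned 15).
- p1 = 0.368: d = 0.367, p̄ = 0.27625, m = (1.7528 + 0.4085)²/0.4041 = 11.560, n0 = 14.973, vaccinees = 44.92 (planned 45).

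Solved for the rate at exactly 15 vs 5 and 45 vs 15, the formula gives 73.4% and 36.7%. One method with the section's own inputs therefore gives both figures. Nearby variants do not: one-sided corrected gives 66.2% and 31.2%, two-sided uncorrected 61.2% and 30.5%.

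**2. What Fisher's exact test rejects.** With no control events, which is nearly always the case (0.999^5 = 0.995; 0.999^15 = 0.985), the one-sided p for x events among n1 vaccinees and n0 controls is C(n1, x)/C(n1+n0, x).

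| Vaccinees with event, controls 0 | One-sided p | Two-sided, tables no more probable than observed | Two-sided, doubled |
|---|---|---|---|
| 11 of 45 | 0.0296 | 0.0505 | 0.0592 |
| 12 of 45 | 0.0206 | 0.0269 | 0.0411 |
| 9 of 15 | 0.0298 | 0.0379 | 0.0596 |
| 10 of 15 | 0.0163 | 0.0325 | 0.0325 |

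The pooled comparison needs 12 events under either two-sided definition. The per-group comparison needs 9 under the first and 10 under the second, which is why its answer depends on the definition.

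**3. Exact power.** Enumerate all tables, reject if p ≤ 0.05, and weight by the two binomial distributions:

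| Definition | 45 vs 15: rate at 80% power | Power at 36.8% | 15 vs 5: rate at 80% power | Power at 73.5% |
|---|---|---|---|---|
| Two-sided, probability-ordered | 31.6% | 94.1% | 66.9% | 92.3% |
| Two-sided, doubled | 31.6% | 93.8% | 73.0% | 81.4% |
| One-sided | 26.9% | 98.4% | 66.9% | 92.3% |

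Differences from the stated figures: pooled 36.8 − 31.6 = 5.2 points; per group 73.5 − 66.9 = 6.6 points, or 73.5 − 73.0 = 0.5 points with doubling. Setting the control rate to 0 instead of 0.1% moves the probability-ordered rates only to 31.4% and 66.8%.

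**The case against.** The strongest reply is that nothing was miscalculated. A standard approximation gives both numbers, and the sentence naming Fisher's test can be read as identifying the planned test, not as claiming that power was enumerated. Exact power is above 80% at both stated rates under every definition in the table, so the trial can detect those rates with at least the power claimed. Section 13.1 also calls the design a compromise between cost and the need to detect safety, and 13.6 treats significance as not pertinent.

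Most of this stands. A reader might infer from the mismatch that 13.1 contains an arithmetic slip or that its figures have no consistent source; the match in step 1 is against that. A reader might also infer that the trial is too small for what it claims; the error runs the other way. Nor do the documents show that the authors used this approximation: that is an inference from the match. Finally, a reader might carry the two rates over to the primary endpoints in 13.4, severe systemic and severe local reactions. Section 13.1 labels its rates as SAE rates and no control rate is given for those reactions, so the documents do not support that use.

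What the reply does not answer is the wording. Section 13.1 calls 36.8% the minimal rate at a power of 0.8, and for Fisher's exact test under the definitions above it is neither minimal nor at 80% power.

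**Conclusion.** The point holds as a minor one about an undocumented power method. The pooled 36.8% is not the 80%-power rate of the named test: that rate is 31.6% under either two-sided definition, and power at 36.8% is 94%. The per-group 73.5% is off only if the two-sided p is probability-ordered (66.9%, power 92%); with doubling it is close (73.0%, power 81%). Both figures err on the conservative side. The result assumes a control rate of 0.1%, rejection at p ≤ 0.05 and two-sided testing; a one-sided test would put the pooled rate further from 36.8%, at 26.9%.

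**What to change.** Change the wording of 13.1 in one of two ways.

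- **Exact values.** State: two-sided Fisher's exact test at 0.05, p-value by summing tables no more probable than the observed one, control rate 0.1%; 80% power at 66.9% (15 vs 5) and 31.6% (45 vs 15). The p-value definition has to be included because the per-group value depends on it.
- **Keep the present figures.** If the authors confirm the source, label 73.5% and 36.8% as two-sided continuity-corrected approximations and add the exact Fisher power: 92% and 94% under the p-value definition above, or 81% and 94% if the one-sided p is doubled.

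The cost is a sentence or two. Sample size, design and analysis do not change.

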13.2. Statistical Methods

Each safety parameter assessed will be compared between vaccine recipients and placebo recipients as determined by Student's T test *and chi-square analyses*. In addition safety parameters will be compared between vaccine dose groups as well as to placebo recipients. In addition each volunteer will serve as their own control for the occurrence of toxicity. Adverse reaction as defined in Appendix 1 and 3 will be reported independent of a statistical association.

Immunogenicity parameters will be compared using response and non-response as well as mean medium and geometric mean titers between vaccine recipients and placebo recipients as determined by Student's T test *and chi-square analyses*. Immunogenicity parameters will be compared between vaccine dose groups as well as between each to placebo recipients. Exploratory analyses will be performed (e.g., examination of frequency distributions, modality of distributions, kurtosis and skewness, etc.) for all variables collected before subjecting the values to statistical analysis. Cross-sectional parametric and non-parametric analyses will be conducted on variables exhibiting normal and non-normal distributions, respectively, to examine differences and trends among treatment categories.

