The toxicology studies showed that repeated intramuscular vaccinations with 300 or 900 µg FLSC (with aluminum phosphate adjuvant) was well tolerated in rabbits (up to 5 administrations) and cynomolgus monkeys (up to 4 administrations). The majority of the effects observed in the rabbit toxicity study can be attributed to general inflammation occurring with intramuscular vaccine administration and/or an active immune response towards the antigen. No deleterious effects on the immune system were detected in the cynomolgus monkey with repeat administration of up to 900 µg FLSC (with aluminum phosphate adjuvant). Of most concern is the potential test article related reduction in platelet count with FLSC; however, this finding only occurred in the rabbit with repeat administration of the high dose of FLSC (900 µg), which is 12-fold greater than the proposed starting dose of 75 µg FLSC in the clinic and 3-fold greater than the proposed maximum clinical dose of 300 µg FLSC. Thus, the safety risk of 4 intramuscular administrations of FLSC (with aluminum phosphate adjuvant) to the patient is low.

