6.1.1.3. Study Evaluations

See also the Schedule of Assessments in [Table 4](#).

1. Study Visit 0, Day –30 to Day –3 (Week –4 to 0): Screening Visit

A screening evaluation will be performed within 3-30 days of the first immunization to determine eligibility for the study and to collect blood for baseline safety evaluation and immunological exams.

- a. Obtain informed consent for study prior to screening
- b. Obtain and record medical history including allergies, medications, and concomitant illnesses, and review of systems
- c. Counsel volunteer regarding avoiding HIV risk behaviors
- d. Perform complete physical examination, including vital signs, temperature, weight and height.
- e. Collect blood for CBC with differential, serum chemistries, liver function tests (including AST, ALT, alkaline phosphatase, total bilirubin), PT/PTT, CD4 cell count, Hepatitis B surface antigen, Hepatitis C antibody, HIV-1 ELISA/Western Blot, HIV-1 quantitative RNA PCR, and, in women, serum human chorionic gonadotropin (HCG) assay (See [Table 4](#) and [Section 11](#)).
- f. Collect urine for urinalysis
- g. Collect blood for baseline immunologic exams (See [Table 5](#) and [Section 12](#))

2. Study Visit 1, Day 0 (Week 0): First Immunization

- a. Obtain interim medical history since screening visit
- b. Perform physical examination, including vital signs, temperature, weight and height.
- c. Conduct urine pregnancy test (female volunteers).

If volunteer continues to meet inclusion/exclusion criteria he/she will be given a volunteer number, randomized, and the following will be done:

- d. Collect blood for safety labs (CBC with differential, serum chemistries, LFT's, CD4 cell count, and Quantitative HIV-1 RNA PCR) ([Table 4](#), [Table 5](#) and [Section 11](#)).
- e. Collect blood for immunologic studies ([Table 4](#) and [Table 5](#) and [Section 12](#)).
- f. Administer first injection of the study vaccine as an intramuscular injection in the deltoid muscle as per [Section 9.5](#).
- g. Record vital signs and examine injection site for local reactions at 15 and 30 minutes post-injection.
- h. Observe and instruct while volunteer takes own temperature and assesses local reactions (as a guide for subsequent evaluations at home).
- i. Counsel volunteer regarding avoiding HIV risk behaviors
- j. Dispense diary for immunization reactions ([Appendix 1](#)) and digital thermometer. Give instructions for diary completion and thermometer use.

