APPENDIX 2. TABLE FOR GRADING SEVERITY OF ADULT ADVERSE EXPERIENCES

(Adapted from the ACTG and AVEG tables)

ABBREVIATIONS: Abbreviations utilized in the Table:

ULN = Upper Limit of Normal	LLN = Lower Limit of Normal
Rx = Therapy	Req = Required
Mod = Moderate	IV = Intravenous
ADL = Activities of Daily Living	Dec = Decreased

ESTIMATING SEVERITY GRADE

For abnormalities NOT found elsewhere on the Table, use the scale below to estimate grade of severity:

GRADE 1 Mild	Transient or mild discomfort; no limitation in activity; no medical intervention/therapy required
GRADE 2 Moderate	Mild to moderate limitation in activity - some assistance may be needed; no or minimal medical intervention/therapy required
GRADE 3 Severe	Marked limitation in activity, some assistance usually required; medical intervention/therapy required, hospitalizations possible
GRADE 4 Life-threatening	Extreme limitation in activity, significant assistance required; significant medical intervention/therapy required, hospitalization or hospice care probable

SERIOUS OR LIFE-THREATENING AEs

ANY clinical event deemed by the clinician to be serious or life-threatening should be considered a grade 4 adverse experience. Clinical events considered to be serious or life-threatening include, but are not limited to:

seizures, coma, tetany, diabetic ketoacidosis, disseminated intravascular coagulation, diffuse petechiae, paralysis, acute psychosis

MISCELLANEOUS

- > When two values are used to define the criteria for each parameter, the lowest values will occur first.
- > Parameters are generally grouped by body system.
- > Some protocols may have additional protocol specific grading criteria.

PARAMETER	GRADE 1 MILD	GRADE 2 MODERATE	GRADE 3 SEVERE	GRADE 4 POTENTIALLY LIFE THREATENING
HEMATOLOGY				
Hemoglobin	8.0 g/dL - 9.4 g/dL	7.0 g/dL - 7.9 g/dL	6.5 g/dL - 6.9 g/dL	<6.5 g/dL
Absolute Neutrophil Count	1000 - 1500/mm ³	750 - 999/mm ³	500 - 749/mm ³	<500/mm ³
Platelets	75,000 - 99,000/mm ³	50,000 - 74,999/mm ³	20,000 - 49,999/mm ³	<20,000/mm ³
Prothrombin Time (PT)	>1.0 - 1.25 x ULN	>1.25 - 1.5 x ULN	>1.5 - 3.0 x ULN	>3 x ULN
PTT	>1.0 - 1.66 x ULN ULN	>1.66 - 2.33 x ULN	>2.33 - 3.0 x ULN	>3.0 x ULN
Methemoglobin	5.0 - 10.0%	10.1 - 15.0%	15.1 - 20.0%	>20%
CHEMISTRIES				
SODIUM				
Hyponatremia	130 - 135 meq/L	123 - 129 meq/L	116 - 122 meq/L	<116 meq/L
Hypernatremia	146 - 150 meq/L	151 - 157 meq/L	158 - 165 meq/L	>165 meq/L
POTASSIUM				

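### Section 13.2 plans no baseline-relative platelet comparison between arms; if its t test is run on raw counts, power in the per-dose comparisons is low

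*Combined protocol and SAP*

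**What the plan says.** Section 13.2 sets the general safety analysis: "Each safety parameter assessed will be compared between vaccine recipients and placebo recipients as determined by Student's T test", together with chi-square tests. It also compares dose groups with each other and with placebo. It gives no scale (raw or change), no visit and no baseline for the t test. It then adds: "In addition each volunteer will serve as their own control for the occurrence of toxicity". That shows a within-person intent, but it concerns whether toxicity occurs and defines no between-arm measure.

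Section 13.4 makes severe systemic and local reactions the primary endpoints and compares safety parameters "as determined by Fisher exact test with a Type I error of no greater than 5" percent. Section 13.6 says: "Level of significance is not pertinent to this trial as it is a Phase 1 safety and immunogenicity trial".

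On platelets, Section 4.4.2 states: "Of most concern is the potential test article related reduction in platelet count with FLSC". It qualifies this at once: "this finding only occurred in the rabbit with repeat administration of the high dose of FLSC" (900 µg, three times the top clinical dose), and rates the overall risk as low. Appendix 2 starts platelet Grade 1 at "75,000 - 99,000/mm"³.

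The baseline data exist. Section 6.1.1.3 takes a CBC at screening, and at Day 0 before injection: "Collect blood for safety labs (CBC with differential, serum chemistries". Section 9.5 confirms that scheduled evaluations precede the injection. Section 11.1.5 includes platelets in the CBC. A percent-decline rule exists for CD4 (Section 6.4.1) but not for platelets.

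**The concern.** Platelet counts differ more between healthy people than within one person over time, at least on the variability assumed below. A t test on raw post-dose counts carries that between-person spread into its error term; a comparison relative to own baseline removes most of it. With only 5 placebo recipients per dose group the difference is large.

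Safety is the primary objective, and safety is one of the grounds for choosing the dose to take forward (Sections 4.2 and 12.2.5). The animal signal appeared only at the high dose, so the per-dose contrast matters most, and it is also the smallest. DSMB reviews are blinded by default (Section 11.6), so the final analysis is the planned place for comparing arms.

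**Working it through.** **The plan's own figures.** Section 13.1 gives minimal detectable SAE rates of 73.5% (15 vs 5) and 36.8% (45 vs 15). The continuity-corrected two-proportion formula, with two-sided 0.05, power 0.8, control rate 0.001 and 3:1 allocation, gives 73.4% and 36.7%, so they reproduce. They concern SAE rates. The plan gives no power for any laboratory parameter.

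**Inputs from the documents.** 15 vaccine and 5 placebo recipients per dose group; 45 and 15 overall; alpha 0.05; Grade 1 ceiling 99,000/mm³.

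**Assumed inputs (not in the documents).** Median 250,000/mm³; between-person CV 20–25%; within-person CV 6–10%; lognormal values; one post-dose visit; two-sided test; baseline the mean of screening and Day 0. The size of the rabbit fall is not given, so 10–20% is also an assumed range.

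**Formulas (log scale).** Let B = ln(1 + between-person CV²) and W = ln(1 + within-person CV²).
- SD of a single post-dose value: √(B + W).
- SD of the log ratio to a two-value baseline: √(W + W/2) = √(1.5W).
- Noncentrality: −ln(1 − fall) / [SD × √(1/n₁ + 1/n₂)].

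**Worked case: 15% fall, 15 vs 5, CVs 20% and 10%.** B = 0.0392 and W = 0.00995. The two SDs are √0.0492 = 0.222 and √0.0149 = 0.122. The effect is −ln 0.85 = 0.1625, and √(1/15 + 1/5) = 0.516. Noncentrality is 0.1625/(0.222 × 0.516) = 1.42 without baseline and 0.1625/(0.122 × 0.516) = 2.58 with it. On 18 degrees of freedom, power is about 27% and 68%.

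**Simulation (20,000 trials per scenario; t test on raw counts vs t test on log ratio to baseline):**

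| Comparison | Fall | Raw counts | Change from baseline |
|---|---|---|---|
| 15 vs 5 | 10% | 13–18% | 35–75% |
| 15 vs 5 | 15% | 22–33% | 68–98% |
| 15 vs 5 | 20% | 37–54% | 92–100% |
| 15 vs 15 pooled placebo | 10% | 18–27% | 62–97% |
| 15 vs 15 pooled placebo | 15% | 36–54% | 94–100% |
| 15 vs 15 pooled placebo | 20% | 59–80% | about 100% |
| 45 vs 15 | 10% | 28–40% | 81–100% |
| 45 vs 15 | 15% | 53–74% | 99–100% |
| 45 vs 15 | 20% | 79–95% | about 100% |

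With no fall, both tests reject about 5%. Regressing log post-dose count on log baseline gives 67–97% for a 15% fall at 15 vs 5, close to the change analysis.

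**Precision.** The 95% CI for the vaccine/placebo ratio extends either side by these factors:
- 15 vs 5: 1.25–1.33 without baseline, 1.08–1.14 with it.
- 15 vs 15: 1.17–1.22 and 1.06–1.10.
- 45 vs 15: 1.13–1.17 and 1.04–1.08.

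**Sensitivity (15% fall, 15 vs 5).** At within-person CV 15%, power rises from 20–25% to about 37%. At CV 20% it rises only from 18–21% to 23–24%. Change loses to raw counts once 1.5W exceeds B + W, that is W > 2B, a within-person CV above about 29–36%. A separate normal model (mean 250, SD 50–60, in thousands/mm³; single baseline) with within-person correlation 0.8 gives 21–28% raw and 44–58% on change. At correlation 0.5 with a single baseline there is no gain.

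**Grading, a separate matter.** From 250,000, reaching 99,000 needs a fall of 1 − 99/250 = 60%. If a 15% fall persisted through all 13 post-dose visits, the chance that any of 15 vaccinees is ever graded is 1–15%. Fisher's exact test would need 9 of 15 vs 0 of 5 graded (p = 0.038).

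**The case against.** The strongest reply is that nothing in Section 13.2 says raw counts. The own-control sentence sits in the same paragraph, and Section 11.2.1.1 defines an adverse event as a change that can be in a laboratory result. A reader might infer that the plan commits to raw counts; the documents do not support that. What stands is that the scale is open and that no between-arm measure of change is named.

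A reader might also infer that any 10–20% fall would be missed. That is too strong: a 20% fall shared by all doses has about 79–95% power on raw counts at 45 vs 15, and up to 80% for one dose against pooled placebo. That pooled result does need the fall at every dose, whereas the animal finding was confined to the high dose.

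Nor does rare grading follow from Section 13.2. It follows from the Appendix 2 cut-offs, which flag clinically low counts, and a baseline-relative analysis would not alter it.

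The clinical weight is limited. From 250,000, a 10–20% fall leaves 200,000–225,000, and the protocol rates the risk low. The DSMB sees laboratory data about every three months and before each escalation, and can unblind. These points hold down the importance of the gap. They do not supply the missing comparison.

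**Conclusion.** The point holds in a limited form. Section 13.2 names a between-arm test without using baseline values already collected, for the laboratory parameter carrying the protocol's leading nonclinical signal. If the test is run on raw counts, the per-dose comparisons are weak for a 15% fall: about 22–33% power at 15 vs 5 and 36–54% at 15 vs 15, where change from baseline would give 68–98% and 94–100%.

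These figures rest on assumed platelet variability. The headline CVs imply a within-person correlation of about 0.80–0.94, and the advantage at 15 vs 5 nearly disappears at a within-person CV of 20%. If change from baseline was always intended, the amendment only records it. It is worth making because it costs little; it does not show that the trial is unsafe or that large falls would go unseen.

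**What to change.** Add to Section 13.2: *Platelets will be compared between arms as the log ratio to own baseline (mean of the screening and Day 0 pre-injection values), or as log post-dose count adjusted for log baseline, on Days 14, 42, 70 and 182. Vaccine/placebo ratios with 95% CIs will be reported for each dose against its own placebo recipients, for each dose against pooled placebo, and for all vaccinees against pooled placebo. These are estimates and not significance claims.* Choose one of the two forms before the codes are broken.

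The days are two weeks after each injection, when a CBC is already scheduled, so there are no new samples or visits. Section 13.9 gives the route: consult a statistician and obtain sponsor approval. Treating neutrophils the same way is optional.

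The cost is more output: 4 visits × (3 + 3 + 1) comparisons = 28 estimates, with about 28 × 0.05 = 1.4 nominal false positives expected if there is no effect. That is why estimates with CIs are preferable, and this fits Section 13.6. Pooled placebo recipients were enrolled at different times and received different saline volumes, so the 15 vs 5 result should stand beside the pooled one. Graded values would still be reported under Appendix 2.
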